4.6. Subject Discontinuation from the Study

Subjects will be informed that they are free to withdraw from the study at any time and for any reason.

The investigator may remove a subject from the study if, in the investigator's opinion, it is not in the best interest of the subject to continue the study. Examples of other reasons subjects may be discontinued from the study are a change in compliance with an inclusion or exclusion criterion, occurrence of AEs, occurrence of pregnancy or use of a prohibited therapy. Notification of discontinuation will immediately (within 24 hours) be made to the Aclaris Therapeutics, Inc. study monitor.

In case of premature discontinuation of study participation, efforts will be made to perform all final study day assessments. The date the subject is withdrawn from the study and the reason for discontinuation will be recorded on the subject's case report forms (CRFs). All withdrawn subjects with ongoing AEs will be followed as appropriate (Section 7.2.1).

The study may be discontinued at the discretion of the investigator or Aclaris Therapeutics, Inc. Some examples of reasons for discontinuation are the occurrence of the following:

- Increased frequency, severity or duration of known AEs
- Medical, regulatory or ethical reasons affecting the continued performance of the study
- Difficulties in the recruitment of subjects.

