4.8. Replacement Subjects

Subject enrollment will continue until approximately 36 subjects have been randomized. Subjects who are randomized and do not complete the study will not be replaced.

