At Visit 5 any target lesion that has a PLA grade of >0, and ONLY target lesions that have a PLA grade of >0, must receive a retreatment study medication application UNLESS the target lesion:

- **Has a Visit 5 pre-application LSR grade of 3 (severe) for any sign or symptom**
- **Is, in the investigator's opinion, not appropriate for a retreatment study medication application.**

All Visit 5 retreatment applications will be terminated for all subjects if 4 or more subjects discontinue from the study due to study medication related AEs.

At Visit 5, for target lesions that require retreatment, a staff member, other than the investigator, will perform the application following the instructions above, using a different vial from the vial used for the Visit 2 application.

The investigator is prohibited from access to any study procedure or document that shows the study medication identity except in cases of a medical emergency (Section [5.10.2](#)).

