6.1.2. Physician's Lesion Assessment (PLA)

The PLA must be performed with the subject standing.

The investigator must perform the PLA evaluation ONLY AFTER the subject performs the SSA and PRIOR to the Signs of Seborrheic Keratosis (SSK). The subject and the investigator must not discuss the subject's SSA grade.

The PLA is the investigator's assessment of the average overall severity of seborrheic keratosis on each target lesion at a particular time point, and is based on the investigator's clinical experience evaluating SK lesions on subjects with similar skin types. The investigator should NOT refer to any other assessments to assist with this evaluation.

The PLA grade must be ≥ 2 at Visit 1 for the subject to be enrolled and must be ≥ 2 at Visit 2 for the subject to be randomized.

At every study visit, the investigator will assess each seborrheic keratosis target lesion and report the one integer that best describes the average overall severity of each using the following scale. For this evaluation the subject must stand in a position similar to the position used for the SSA (Section [6.1.1](#)). At Visit 2, and if appropriate Visit 5, the investigator must perform the PLA prior to the study medication application:

Physician's Lesion Assessment	
Grade	Descriptor
0	Clear: no lesion, normal skin
1	Mild: lesion is barely evident on examination
2	Moderate: obvious lesion
3	Severe: severe lesion, prominent

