9. STATISTICAL ANALYSES

9.1. Statistical Analysis of Clinical Indices

The primary effectiveness analyses will be pairwise comparisons between Vehicle and each active study medication, based on mean change from Visit 2 PLA, using a repeated-measures Analysis of Covariance model suitable for the study design. Study medication concentration is the within-subject independent variable. The Visit 2 score will be the covariate. The primary analysis visit will be Visit 9. An exploratory dose-response analysis may be conducted across concentrations to evaluate a concentration trend, as well as an exploratory longitudinal analysis across visits to evaluate trends over time.

Secondary efficacy analyses will include a similar analysis of SSA, SSK and other evaluations suitable for analysis as continuous variables. Separate primary and secondary effectiveness analyses at each post-baseline visit will be conducted. In addition, secondary analyses will be performed on proportion of PLA and SSA responders, where a subject will be considered a responder if the Visit 9 score is 0. A similar analysis will be done at Visit 5. Chi-square will be used to analyze differences in response rates under the assumption that lesions within a subject may be treated independently, along with a repeated-measures logistic regression model applied as an optional exploratory analysis method.

For all analyses two-tail alpha will be set at 0.05 with no adjustment for multiplicity due to the exploratory nature of the study. The Intent-to-Treat (ITT) population, defined as subjects with data for both Visit 2 and at least one post-Visit 2, will be the primary analysis population, supplanted by analyses of the Per-Protocol (PP) population defined as ITT subjects with no missing effectiveness data and no major protocol violations. ITT population analyses will use last-observation-carried-forward to impute missing post-Visit 2 data.

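### Last observation carried forward lets a PLA score from Day 8 to 22, before any retreatment, stand as the Visit 9 result in the primary ITT analysis

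*Combined protocol and SAP*

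**What the plan says.** Protocol Section 9.1 bases the primary effectiveness analysis on mean change in PLA from Visit 2, each active concentration against vehicle, and adds: "The primary analysis visit will be Visit 9". The primary population is ITT, "defined as subjects with data for both Visit 2 and at least one post-Visit 2". For missing values, "ITT population analyses will use last-observation-carried-forward to impute missing post-Visit 2 data". The supporting per-protocol set is limited to "ITT subjects with no missing effectiveness data and no major protocol violations". Section 9.1 also plans ITT analyses at every post-baseline visit and allows an exploratory longitudinal analysis, which is optional.

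On timing, Section 6.1.2 says: "At Visit 2, and if appropriate Visit 5, the investigator must perform the PLA prior to the study medication application". Under Section 5.7.6, a lesion with PLA above 0 at Visit 5 "must receive a retreatment study medication application UNLESS the target lesion" meets one of two exceptions.

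On loss, Section 4.1 plans about 36 subjects with a goal of 32 completers. Section 4.8 says: "Subjects who are randomized and do not complete the study will not be replaced". For early discontinuation, Section 4.6 says that "efforts will be made to perform all final study day assessments".

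**The concern.** Visits 3, 4 and 5 fall on Days 8, 15 and 22; Visit 9 falls on Day 78. A subject last seen at Visit 3, 4 or 5 has PLA scores after one application only. LOCF enters the last of them as the outcome of a regimen of up to two applications, at least 56 days (78 - 22) after it was scored.

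A subject who leaves the study normally takes all four lesions along, so unequal dropout between medications is not the problem. The problem is that the active-minus-vehicle difference may change between the carried visit and Visit 9. If it grows after retreatment, LOCF pulls the estimate toward its early value. If lesions recur, LOCF overstates the effect. LOCF is therefore not reliably conservative.

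Nothing else in the plan corrects the primary estimate:
- Withdrawal assessments make the carried score less stale, but they are made when the subject leaves, and the plan does not say how they map to Visit 9.
- The per-protocol set is a complete-case analysis, which is biased if leaving depends on early response.
- The by-visit ITT analyses follow the same LOCF rule.
- No other missing-data method is specified.

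**Working it through.** The plan gives no figure for the effect of missing data, so there is none to reproduce. The size has to be shown as a range.

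**From the documents.** About 36 randomized and a goal of 32 completers (Sections 4.1, 4.8) imply a loss of 4/36 = 11.1%. PLA is an integer from 0 to 3, scored on four lesions at seven post-baseline visits (Sections 5.2, 6.1.2). Expected response rates are 60% for the best active and 10% for vehicle (Section 9.3), a difference of 50 points.

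**Assumed.** True Visit 9 difference D9 = -1.2 grade; SD of the within-subject difference 0.9; correlation between visits 0.7; early difference De from -0.3 to -1.5; 2 or 4 subjects carried. Four is the most the planned loss allows: all four must have a Visit 3 score and leave before Visit 6.

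**Formula.** With a fraction f carried and random loss, LOCF estimates (1 - f) x D9 + f x De, so bias = f x (De - D9).

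**f = 4/36, lost before retreatment** (coverage from 3,000 simulated trials per setting):

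| De | Bias = 4/36 x (De + 1.2) | LOCF estimate | Effect | Coverage |
|---|---|---|---|---|
| -0.3 | +0.100 | -1.10 | 8% attenuation | 91.8% |
| -0.6 | +0.067 | -1.13 | 6% attenuation | 92.6% |
| -0.9 | +0.033 | -1.17 | 3% attenuation | 95.2% |
| -1.2 | 0 | -1.20 | none | – |
| -1.5 | -0.033 | -1.23 | 3% inflation | – |

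With 2/36 lost, the bias is 2/36 x 0.9 = 0.050 down to 2/36 x 0.3 = 0.017, or 4% to 1%, with coverage of 94% to 95%. With 4/36 lost after retreatment, LOCF gives -1.16 to -1.17.

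**Loss that depends on a poor early response** (De from -0.3 to -0.9). LOCF gives -1.09 to -1.16. Completers alone give -1.29, with coverage of about 91%. A repeated-measures likelihood model on the same within-subject differences gives -1.20 with 95% to 96% coverage in each case. At De = -0.3 the LOCF standard error is 0.156 against 0.153 for that model, so the fault is bias and not an understated error.

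**Lesion-level check.** Integer PLA, 36 x 4 lesions x 7 visits, AR(1) residuals, 4 subjects lost before retreatment, true Visit 9 difference -1.08, 2,000 trials per setting. The mixed model had random subject and lesion effects with independent residuals:

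| Loss | De | LOCF (coverage) | Mixed model (coverage) |
|---|---|---|---|
| Random | -0.26 | -0.99 (92.3%) | -1.08 (96.6%) |
| Random | -0.53 | -1.02 (93.8%) | -1.08 (96.2%) |
| Response-dependent | -0.26 | -0.98 (93.0%) | -1.08 (96.2%) |

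The formula agrees: 4/36 x (1.08 - 0.26) = 0.09, and -1.08 + 0.09 = -0.99. Completers gave -1.13 (93.2%) in the last setting. All 6,000 mixed-model fits converged.

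**With an AR(1) residual in the fitted model.** A smaller lesion-level simulation (about 160 to 190 trials per setting, true difference -1.13) gave LOCF -1.02 and -0.99 with coverage of about 90% to 92%. The AR(1) mixed model gave -1.11 to -1.12 with 96% to 97% coverage, converged in every trial, and lost nothing when the difference was flat.

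**Responder scale.** At f = 4/36 and a final difference of 50 points, carried differences of 0, 25, 40, 50 and 60 points give biases of -5.6, -2.8, -1.1, 0 and +1.1 points; for example, 4/36 x (0 - 50) = -5.6. In the worst of these, chi-square power with 36 lesions per medication falls from 99.8% to 99.1%.

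**The case against.** The strongest reply is that the effect is too small to change a conclusion. The largest bias in the main simulation is about 0.1 grade, or 0.10/0.156 = 0.64 of a standard error. It requires all four implied non-completers to leave between Visit 3 and Visit 6 and the difference to quadruple afterwards. Type I error is intact: with no difference at any visit and 4/36 lost early, it was 4.95% under random loss and 4.96% under response-dependent loss. The study is exploratory and from a single center. This stands as a limit on importance, but it does not make LOCF the better estimator, and estimation matters in a study meant to give initial effectiveness data on three concentrations.

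A second reply is that the per-protocol analysis partly covers the gap. Under random loss, complete cases are unbiased. Under response-dependent loss, LOCF and completers err in opposite directions in these settings, so a gap between them would be a warning. That is fair, but a warning does not give a corrected primary estimate.

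Third, genuine Visit 9 data also include lesions with one application, because cleared lesions, excepted lesions and refusals are not retreated (Sections 5.7.6, 5.7.8). This is true, and it reduces the mismatch. It does not turn a Day 8 score into a Day 78 score.

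Fourth, the mixed model assumes that loss depends only on observed data, and no simulation tested loss that depends on unseen outcomes. That caveat stands; keeping LOCF as a sensitivity analysis covers it only in part. The evidence for the AR(1) version also rests on fewer trials than the evidence for the simpler one.

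**Conclusion.** The concern holds. Under Section 9.1 a score from Day 8 to 22, taken before any retreatment, can be analyzed as the Visit 9 result, and nothing else planned repairs the primary estimate. The bias is conditional and modest. With 4/36 lost before retreatment and an assumed final difference of -1.2, it runs from 8% attenuation to 3% inflation over the early differences examined, with coverage of about 92% at worst. It is zero if the difference is flat and loss is random.

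The size rests on assumed values for the final and early differences, the SD, the correlation between visits and the timing of loss, none of which the documents give. The change is recommended because a better analysis of data already collected is available; the trial's conclusion is not shown to depend on it.

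**What to change.** In Section 9.1, make the primary analysis a likelihood-based repeated-measures mixed model on all observed PLA changes at Visits 3 to 9, without imputation. Include medication, visit, medication-by-visit and Visit 2 PLA, and take the Visit 9 active-minus-vehicle contrasts from it.

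Name the covariance in advance: random subject and lesion-within-subject effects with an AR(1) residual across visits (4 parameters). An unstructured matrix for 4 x 7 = 28 scores would need 28 x 29/2 = 406 parameters, far too many for 36 subjects. If the model does not converge, use the two random effects with independent residuals (3 parameters).

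State the missing-at-random assumption, say how withdrawal assessments map to visits, and keep LOCF as a sensitivity analysis.

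The cost is analysis-plan wording and modest programming, with no new data or visits. The downside is reliance on a simple covariance structure with 36 subjects; the 3-parameter fallback gave slightly conservative coverage, about 96%, in simulation.

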9.2. Statistical Analysis of Safety Data

Descriptive statistics will be calculated on the safety parameters using the intent-to-treat population, defined as those subjects who were randomized and received at least one study medication application. The proportion of subjects with treatment-emergent adverse events will be tabulated and presented by treatment and Medical Dictionary for Regulatory Activities (MedDRA) System Organ Class. Vital signs, clinically-relevant ECG results, LSR scores and clinically-relevant abnormal laboratory results will also be tabulated and presented by study medication and abrasion cohort. No inferential testing will be performed.

Data from all randomized subjects will be presented and summarized. Safety summaries by study medication group will include listings by study medication of adverse events incidences within each MedDRA System Organ Class, and changes from pre-application values in vital signs. Adverse event summaries will be presented by study medication showing the proportion of subjects experiencing adverse events, both overall and by MedDRA System Organ Class.

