1. SYNOPSIS

Title:

A Randomized, Double-Blind, Vehicle-Controlled, Within Subject Comparison Study of the Safety, Tolerability and Effectiveness of A-101 Topical Solution in Subjects with Seborrheic Keratosis.

Objectives:

The main objective of this study is to evaluate the safety and effectiveness of A-101 (hydrogen peroxide) Solution 25%, 32.5% and 40% when applied to individual seborrheic keratosis (SK) target lesions on the back compared with a matching A-101 Solution Vehicle.

Methodology/Study Design:

The duration of study participation is anticipated to be a maximum of 95 days per subject. This includes the up to 14-day screening period, a visit for a required study medication application, a 21-day no treatment period, a visit for an optional study medication retreatment application, a 56-day no treatment follow-up period and a maximum allowable 4-day Visit 9 visit window. Study visits are:

- Visit 1 (Day -13 to 0) enrollment; start screening period
- Visit 2 (Day 1) randomization; study medication application
- Visit 3 (Day 8) no treatment follow-up
- Visit 4 (Day 15) no treatment follow-up
- Visit 5 (Day 22) follow-up visit where target lesions that meets the retreatment criteria will receive a second study medication application
- Visit 6 (Day 29) no treatment follow-up
- Visit 7 (Day 43) no treatment follow-up
- Visit 8 (Day 57) no treatment follow-up
- Visit 9 (Day 78) no treatment follow-up; end of study.

During Visit 1 the investigator will, for each subject, identify 4 individual SK lesions (target lesions) on the back for treatment, perform an electrocardiogram (ECG) and collect blood samples for clinical laboratory safety tests to determine the subject's eligibility for randomization. Subjects may have more than 4 SK lesions on the back, or on other body surfaces, but only the target lesions on the back will be evaluated and treated.

During Visit 2, eligible subject's target lesions will be randomized, each to receive 1 study medication (a unique study medication for each target lesion) and then the study medication applications will be performed. Every eligible subject will receive all 4 of the study medications.

At Visits 3 and 4, subjects will be seen for a no treatment follow-up.

At Visit 5, subjects will be seen for follow-up and any target lesion that meets the re-treatment criteria (*i.e.*, Physician's Lesion Assessment [PLA] >0) will receive a second study medication application.

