16. Confirm subject is eligible for randomization, discharge from the study subjects who are not eligible for randomization (Section 4.6).

For subjects eligible for randomization the investigator or designee will perform the following procedures:

1. Randomize eligible subjects (Section 5.7.4)
2. An investigational center staff member, other than the investigator, will perform the initial study medication application for all 4 target lesions (Section 5.7.6)
3. Have the subject perform a post-application Local Skin Reaction assessment of the symptoms for each target lesion 10 (\pm 4) minutes after the study medication application to all target lesions is completed (Section 6.2.1)
4. Perform a post-application Local Skin Reaction assessment of the signs for each target lesion 20 (\pm 4) minutes after the study medication application to all target lesions is completed (Section 6.2.1)
5. Monitor the subject for at least 20 minutes after completion of the study medication applications to detect any adverse events (Section 7.2.1)
6. Review the study instructions and restrictions with the subject (Section 5.5)
7. Schedule Visit 3 for Day 8.

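### Section 9.2 tabulates whole-subject safety data by study medication although every subject is assigned all four medications, and it splits tables by an undefined abrasion cohort

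*Combined protocol and SAP*

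**What the plan says.** Section 9.2 (Statistical Analysis of Safety Data) asks for by-medication displays in several places:

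- For four data types: "Vital signs, clinically-relevant ECG results, LSR scores and clinically-relevant abnormal laboratory results will also be tabulated and presented by study medication and abrasion cohort".
- The safety summaries by medication group are to include "listings by study medication of adverse events incidences within each MedDRA System Organ Class, and changes from pre-application values in vital signs".
- The AE summaries are to be "presented by study medication showing the proportion of subjects experiencing adverse events, both overall and by MedDRA System Organ Class".

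The safety population is "defined as those subjects who were randomized and received at least one study medication application". A separate sentence says "Data from all randomized subjects will be presented and summarized". On testing, the section says "No inferential testing will be performed".

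The design is stated elsewhere in the same document. The Synopsis says "Every eligible subject will receive all 4 of the study medications". Under Section 5.3.2 (Visit 2), a staff member "will perform the initial study medication application for all 4 target lesions", and Section 5.7.6 describes the same procedure.

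**The concern.** Lesions, not subjects, are randomized to medication. A by-medication table is valid for anything recorded per lesion. It is not valid for something recorded once per subject, because that subject has been exposed to 25%, 32.5%, 40% and vehicle together. Section 9.2 applies the by-medication layout to both kinds of data and gives no rule for placing a whole-subject result in a column.

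The risk is misreading. A table with active and vehicle columns invites comparison. If the columns match only because the same people fill each one, a reader may take the match as evidence that an active concentration behaves like vehicle. The overall AE row is harder still to read. It mixes lesion AEs, which can differ between columns, with non-lesion AEs, which cannot, and nothing in the row shows the proportions.

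The abrasion cohort is a separate defect in the same section. It names a subgroup that the rest of the document does not contain.

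**Working it through.** The plan gives no figure to reproduce here. The check compares the level at which each safety variable is recorded with the level at which medication is assigned, and then works out what the tables would show.

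**Level of recording**

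| Safety variable | Recorded per | Source | Attributable to one medication? |
|---|---|---|---|
| Vital signs | subject | 6.2.2 | No |
| ECG | subject | 6.2.3 | No |
| Laboratory results | subject | 6.2.4 | No |
| AE with no target lesion number | subject | 7.1.1 | No |
| AE with a target lesion number | lesion | 7.1.1 | Yes |
| LSR scores | lesion | 6.2.1 | Yes |

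Vital signs, ECG and laboratory samples are scheduled at Visit 1, at Visit 2 before randomization, and at Visit 9. The only scheduled reading after application is therefore Visit 9, or the final assessment attempted when a subject leaves early (Section 4.6). By then a fully treated subject has received all four medications. Visit timing cannot separate them, because all four are first applied at Visit 2.

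**What the columns would show**

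Inputs: N = 36 randomized (Section 4.8, approximate) and a goal of 32 completers (Section 4.1). The number k of subjects with at least one non-lesion AE is not in the documents; I assume 4, 8 and 12. I also assume that all four medications were applied to every subject and that each subject is counted under every medication received. The second is the literal reading of Section 9.2.

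Proportion in each column = k / N. Active minus vehicle = k/N − k/N = 0. Entries across the table = 4k.

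| k (assumed) | Each of the four columns | Active minus vehicle | Entries in table | Subjects behind them |
|---|---|---|---|---|
| 4 | 4/36 = 11.1% | 0 | 16 | 4 |
| 8 | 8/36 = 22.2% | 0 | 32 | 8 |
| 12 | 12/36 = 33.3% | 0 | 48 | 12 |

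The zero does not depend on k. The same holds for vital signs: the mean change in a column is the sum of the subjects' changes divided by their number, and the same subjects stand in all four columns, so the four means are identical. With 32 final readings the table holds 32 × 4 = 128 entries; with 36 it holds 36 × 4 = 144. Since 32 is a goal, fewer readings are possible.

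The safety population requires only one application, so a partly treated subject would enter fewer columns. Small differences between columns could then arise, reflecting who was partly treated rather than any effect of a medication.

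The other way to fill the table is to place each whole-subject result in a single column. Nothing recorded supports such a choice, so it would be arbitrary.

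**Abrasion cohort**

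The term occurs only in Section 9.2. The study design (5.1), flow chart (5.2), treatment assignment and randomization (5.7.3, 5.7.4) and application procedure (5.7.6) contain no abrasion step, cohort or stratum. Preparation of the lesion is cleansing with alcohol. The split is requested for four data types: vital signs, ECG, LSR and laboratory results.

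**The case against.** Several points can fairly be made for the plan.

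- *Section 9.2 states no counting rule, so equal columns are an inference.* This is true. The figures above hold under the literal reading. The only alternative is arbitrary assignment, which is no better.
- *Under that reading each column shows the correct pooled proportion, merely repeated four times.* This stands. No incidence is falsified. What is lost is any meaning in the comparison between columns, which is the purpose of a by-medication layout.
- *The sentence about all randomized subjects allows a pooled summary.* It allows one, but it does not specify one for these variables and does not remove the by-medication instructions around it.
- *Treatment could mean treatment group.* The Synopsis describes 16 treatment groups built from permutations of the medications. Each group still contains all four, so this reading does not help.
- *Lesion-numbered AEs can be placed correctly.* Agreed. Section 7.1.1 requires the lesion number, so the AE part of the concern covers only AEs without one. Section 9.2, however, does not state a lesion-number rule, and such a rule could not place vital signs, ECG or laboratory results.
- *The tables are descriptive and the study is exploratory.* This limits the consequence. It does not make the tables interpretable, and with no safety testing planned they are the whole safety analysis.
- *A programmer would query or drop the cohort term.* Probably. The by-medication LSR table can be produced without it; only the additional split cannot.

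**Conclusion.** The concern holds. For vital signs, ECG, laboratory results and AEs not tied to a target lesion, the by-medication layout in Section 9.2 does not fit the within-subject design. Followed literally, with all four medications applied, it gives an active-minus-vehicle difference of exactly 0 whatever the true effects. The percentages quoted rest on N = 36 and on assumed values of k; the zero does not.

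The consequence is confined to descriptive safety tables. No test is affected and no data are lost. Clinically relevant abnormalities in vital signs, ECG and laboratory results found after the first application are also reported as AEs (Sections 6.2.2 to 6.2.4). Those AEs generally carry no lesion number, so they meet the same difficulty in the AE table. Safety is part of the main objective in the Synopsis and a secondary objective in Section 3, so the section should be corrected before tables are programmed. The abrasion-cohort split cannot be produced as written.

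**What to change.** Amend Section 9.2 as follows.

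1. Summarize vital signs and their changes, ECG, laboratory results and AEs without a target lesion number once, for all treated subjects, with the statistics already planned. Include final assessments of subjects who discontinue early. Say that this set is the safety population already defined there, since the section also refers to all randomized subjects.
2. Keep by-medication tables for LSR scores and AEs with a target lesion number only. State the counting rule. One workable rule counts an AE with several lesion numbers once under each medication concerned and once in the overall total.
3. Delete the abrasion cohort, or define it if it was intended.

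The cost is wording and table shells. No new data are needed, because the lesion number is already required for lesion AEs under Section 7.1.1, and no study procedure changes.
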